3.3 Randomization

Following baseline assessment, randomization will occur in a 1:1 ratio, stratified by age, gender (men, women), and EuroSCORE (indicative of disease severity), assigning participants either to the intervention group or to usual care. Randomization is completed using the web-based tool Randomizer for Clinical Trials.

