3.6 Sample size and power

As the primary aim of this study is to evaluate feasibility, there is no formal requirement for a formal power calculation.⁶² Sample sizes between 24 and 50 have been recommended.^{63,64} A sample size of 25 patients in each group was chosen as it seems reasonable to provide outcome data in a small sample, and at the same time a sample size large enough to investigate the additional aspects that are being assessed for feasibility⁶⁵ informing a future power calculation for a full-scale RCT.

4. Selection and allocation of participants

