6.2.5 Alcohol cessation intervention

The approach to support patients in zero alcohol intake before surgery is rooted in the recommendations from the Danish Health Authority and the patients are encouraged to completely avoid alcohol intake if the patient is assessed a risky drinker (drinking more than 4 alcohol items per day).⁸⁶ A simple guide of questions and advice will be developed for the adherence support to register challenges and encourage adherence to support minimizing/avoiding alcohol intake. Assessment, counseling, and support sessions will be organized with the social nurse at Rigshospitalet for patients exhibiting hazardous drinking behaviors.

After the initial face-to-face meeting in the pre-clinic participants will receive three web-based sessions with a physiotherapist and one telephone counselling with a nurse per week during the intervention period. Detailed protocols for the face-to face counselling and web-based and telephone calls will be developed before the outset of the study.

7. Study outcome measures

In this CABGpreHAB feasibility study we will explore two types of outcomes: feasibility outcomes and explorative clinical outcomes.

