7.2 Secondary outcome

Secondary outcomes shown in **Table 1**. will assess the patients' responses to the multimodal prehabilitation programme and data will be collected on the following explorative outcomes shown in **Table 2**, measured at baseline, the day before surgery and 30 days after discharge.

Table 1. The patient related tests and outcome measures

Outcome variable	Measurement Instrument	What is the argument for this test or instrument?
TESTS		
Exercise capacity	6MWT	(6MWT) measures total walking distance completed in six minutes. ⁸⁸ Functional exercise capacity assessed as change from baseline by using the (6MWT) according to the American Thoracic Society guidelines. ⁸⁸
Muscle strength	30 seconds sit-to stand	Strength and endurance in leg assessed as change from baseline by 30 sec sit-to stand test. ⁸⁹
Muscle strength	Hand grip strength	The Hand grip strength measures the upper-body physical function assessed by hand grip strength using a hand-held dynamometer. ⁹⁰ Frailty assessed from baseline by Hand grip strength.
Body composition	BIA	Bio-electrical Impedance Analysis (BIA) estimates values for each body percentage, fat mass, fat-free mass, muscle mass and bone mass and total body water are assessed measuring bioelectrical impedance in the body using a Bioelectrical Impedance Analyzer. ⁹¹
Nutritional status	NRS 2002 + BMI, weight, height	Nutritional Risk Screening 2002 (NRS 2002) screening tool is a validated tool attributes scores of different levels of nutritional status to patients based on weight loss, BMI, and food intake, considering disease severity (degree of stress metabolism) and age. It is a toll recommended for detection of undernutrition and the risk of its development in hospital settings. Nutritional status assessed as changed from baseline. ⁷⁸ Body mass index BMI ⁹² at baseline,
Daily physical activity score	SENS® motion accelerometer	The SENS motion® system consist of a single-use miniature, waterproof tri-axial accelerometer, and a dedicated smart phone application. The accelerator will be placed on the lateral side of the patient's thigh at the assessment initial with a small waterproof Band-Aid. The participants will be asked to wear the SENS-accelerometer continuously for minimum four weeks during the intervention period and again post-surgery until end of follow up 30 days post index surgery. Physical activity assessed as changed from baseline by accelerator SENS innovation device. ⁷⁵
QUESTIONNAIRES		

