9.1 Statistical methods

Data analysis will be limited to descriptive summary statistics of the proposed endpoints, and calculation of feasibility measures, enrollment rates and dropout rates within a period. The feasibility analysis will be based on the components of process, resources, management, and scientific approach.⁵⁸ Process: number of eligible patients for enrollment; Successful recruitment rate, rate of adherence to the interventions at each time point; Rate of loss to follow up; Rates of completed questionnaires; Understanding of the questionnaires. Resources: Time to screen and consent patients, Time to conduct baseline and follow-ups; Identification of any challenges related to randomization or data collection; Identification of potential barriers of the preoperative programme. Management: Identification of any challenges related to randomization or data collection; Identification of potential barriers for the intervention. Scientific approach: Estimates of improvement in patient-reported outcomes compared to usual care, patients' response to topics and content in the programme and identification of potentially patient safety issues. As recommended for the analysis of pilot studies⁵⁸ descriptive statistics will be presented as mean and standard deviations (SD) for continuous variables and frequencies and percentages for categorial variables at baseline and follow-ups. Collected data on patient characteristics will be presented in tables. Continuous variables will be displayed as mean (SD), while categorical variables will be presented as number (n) and percentage (%). Descriptive statistics will be used to answer the primary study parameter of feasibility. Feasibility will be presented in tables and based on participation rate (n, %), reasons for nonparticipation (n, %, text), adherence to the prehabilitation program (%), dropout rates (%), reasons for dropout (n, %, text), adverse events (n, %, text). The secondary aim is to evaluate the patients' responses over time in terms of physical activity, muscle strength, functional capacity, body composition, quality of life and symptoms of depression, and anxiety. A repeated measurements analysis will be used to analyze changes over time in continuous variables. *P*- values <0.05 will be considered statistically significant.

10. Ethics

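### Section 9.1 names a repeated-measures analysis of changes over time without mentioning baseline or the stratification factors; in its ordinary form this is less precise than a baseline-adjusted comparison

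*Protocol*

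**What the plan says.** Section 3.3 of the protocol places randomisation after the baseline assessment: "randomization will occur in a 1:1 ratio, stratified by age, gender (men, women), and EuroSCORE".

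Table 1 in section 7.2 words several continuous outcomes as changes. For the walk test it reads "Functional exercise capacity assessed as change from baseline by using the (6MWT"), and the sit-to-stand test, nutritional status, accelerometer activity and SF-12 are described in the same way.

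Section 9.1 is mainly descriptive, with means and SDs at baseline and at the follow-up visits. For the secondary aim it names one model: "A repeated measurements analysis will be used to analyze changes over time in continuous variables". A significance threshold of 0.05 follows. The section also promises estimates of how patient-reported outcomes improve relative to the control arm, so a between-arm estimate is intended. It lists no model terms: not arm, time, their interaction, the covariance structure, baseline or the stratification factors.

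The stakes are limited by the protocol's own description. The opening of section 7 divides the outcomes into "feasibility outcomes and explorative clinical outcomes". Section 3.6 says that "there is no formal requirement for a formal power calculation" and that "A sample size of 25 patients in each group was chosen". Sections 2.2 and 3.6 add that the data are to support the sample size of a later full-scale RCT.

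**The concern.** Baseline values of the outcomes and all three stratification factors are known before allocation, so they can be used in the analysis without collecting anything new. A change score uses the baseline with its coefficient fixed at 1. Estimating that coefficient is at least as efficient in large samples, and clearly better when the correlation between baseline and follow-up is moderate.

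Two things are affected. The between-arm intervals from 25 patients per arm would be wider than the data allow. The variability figure passed to the RCT may also not suit it: the SD of a change is not the residual SD that sizes a baseline-adjusted trial, and 9.1 does not list the correlation needed to convert one into the other.

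**Working it through.** **Inputs.** 25 patients per arm, 50 in all (section 3.6); 1:1 allocation (section 3.3); baseline measured before randomisation (section 3.3). The protocol gives no outcome SD, effect size, baseline-to-follow-up correlation r, or share of variance R² explained by the stratification factors. The values of r and R² below are assumptions. There is no power-based figure to reproduce.

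**Step 1: what the ordinary model estimates.** With arm, time and arm-by-time terms and complete data, the fitted cell means equal the observed cell means under any common covariance structure. The contrast at a follow-up visit is therefore (follow-up mean minus baseline mean, intervention) minus (follow-up mean minus baseline mean, control). This is the difference in mean change scores.

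**Step 2: variances.** Take a common SD σ at both visits. In units of σ² per patient:

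- change score: 2(1 − r)
- baseline-adjusted: 1 − r²
- ratio: (1 − r²) / [2(1 − r)] = (1 + r)/2

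The standard error of the arm difference, in units of σ, is √(variance × 2/25).

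| r (assumed) | Change variance | Adjusted variance | Ratio | SE, change | SE, adjusted | 1/ratio |
|---|---|---|---|---|---|---|
| 0.5 | 1.00 | 0.75 | 0.75 | 0.283 | 0.245 | 1.33 |
| 0.6 | 0.80 | 0.64 | 0.80 | 0.253 | 0.226 | 1.25 |
| 0.7 | 0.60 | 0.51 | 0.85 | 0.219 | 0.202 | 1.18 |
| 0.8 | 0.40 | 0.36 | 0.90 | 0.179 | 0.170 | 1.11 |

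Outside this range the ratio is 0.65 at r = 0.3 and 0.95 at r = 0.9. The last column is the relative sample size that a change-score analysis would need for the same precision.

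**Step 3: check by simulation.** With r = 0.6, 25 per arm and 4,000 runs, the empirical SE was 0.252 for the change score and 0.227 for baseline adjustment. It was also 0.227 for a repeated-measures model that keeps baseline as a response but constrains its mean to be equal in both arms.

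**Step 4: adding age, gender and EuroSCORE.** An approximate variance factor for k = 3 extra terms with n = 50 is (1 − R²)(n − 3)/(n − 3 − k) = (1 − R²) × 47/44:

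- R² = 0: 1.07
- R² = 0.06: 1.00
- R² = 0.10: 0.96
- R² = 0.20: 0.86

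The formula allows for chance imbalance, which stratification reduces, so the cost at low R² is somewhat overstated.

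**Step 5: the pessimistic case for the whole proposal.** Use the same approximation for all four covariates (own baseline plus three factors that explain nothing). The penalty is 47/43 = 1.093. The net ratio to a change score is 0.75 × 1.093 = 0.82 at r = 0.5 and 0.90 × 1.093 = 0.98 at r = 0.8. The gain shrinks but does not reverse in this range. At r = 0.9 it would: 0.95 × 1.093 = 1.04.

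**Step 6: the figure for the RCT.** At r = 0.5 the SD of a change is √1.00 σ = 1.00σ and the baseline-adjusted residual SD is √0.75 σ = 0.87σ. Sizing a baseline-adjusted RCT from the former would inflate the sample size by 1/0.75 = 1.33.

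**The case against.** The strongest reply is that the protocol is silent, not wrong. A reader might infer from 9.1 that the model is unadjusted and that the stratification factors are left out. The text does not say so. It lists no terms at all, and a covariate list for an exploratory model is commonly left to the statistical analysis plan, which is not at hand. Nor does the Table 1 wording settle the estimator: a change score can itself be analysed with baseline as a covariate, and the arm estimate is then the same as adjusting the final value.

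A second reply is that a repeated-measures model need not lose anything, since with a common baseline mean it matches baseline adjustment (step 3). That is correct, but it needs a constraint that 9.1 does not state. The ordinary form of the named analysis does not have it.

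A reader might also infer that omitting the stratification factors necessarily widens the intervals. That is not supported either. If they explain nothing, including them costs a little, and the break-even is at an R² of about 6%, for which the protocol offers no evidence.

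Finally, the clinical outcomes are exploratory, the trial was not sized for a between-arm test, and 9.1 already plans means and SDs at each visit, so the RCT will not receive only a change-score SD. All of this stands, and it limits the weight of the point. The remaining gap is that visit-specific SDs alone do not yield the correlation.

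**Conclusion.** The point holds as a cheap improvement to exploratory outcomes. Section 9.1 and Table 1 together point to an analysis of change whose ordinary form is less precise than a baseline-adjusted one. For an assumed r of 0.5 to 0.8 the adjusted variance is 0.75 to 0.90 of the change-score variance, which makes intervals about 13% to 5% narrower (√0.75 = 0.87, √0.90 = 0.95). With four covariates, three of them useless, the variance ratio is about 0.82 to 0.98.

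These figures rest on assumed correlations, equal SDs at the two visits, complete data and a model with free baseline means. If the analysis plan already constrains or adjusts for baseline, the baseline part of the loss is zero. The stratification factors may bring a gain or a slight cost. The feasibility conclusions are unaffected.

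**What to change.** Add to section 9.1:

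- For each continuous secondary outcome, estimate the between-arm difference with a 95% CI at each post-baseline visit where Table 2 measures it. For the walk test, sit-to-stand and SF-12 that means the day before surgery and day 30. For grip strength and body composition it means the day before surgery only. SOC-13 is scheduled only at baseline and has no such estimate.
- Adjust for the outcome's own baseline value, or keep baseline as a response with its mean constrained equal across arms. Also adjust for age, gender and EuroSCORE, and state whether age and EuroSCORE enter as continuous values or as the categories used for stratification.
- Report the baseline-adjusted residual SD or the baseline-to-follow-up correlation for the RCT sample size, alongside the descriptive means, SDs and changes already planned.

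The cost is wording and about four degrees of freedom per visit (from 50 − 2 = 48 to 44 with complete data and one term per factor). No new data are needed. If precision is a worry because the sample shrinks through dropout, baseline adjustment has the firmer case, since the gain from the stratification factors depends on how prognostic they prove to be.

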2.1 Primary objective

The primary objective of this feasibility study is to determine if it is feasible for patients awaiting elective CABG surgery to participate in a preoperative homebased multimodal prehabilitation intervention. We will evaluate this through completion of the following objectives:

- Assess the proportion of eligible patients that are recruited into the study.
- Assess the suitability of inclusion and exclusion criteria by examining recruitment data.
- Explore reasons for non-consent to study participation.
- Assess the acceptability of the study to patients by measuring recruitment and retention to the study and thorough qualitative interview responses.
- Assess the acceptability of the intervention through qualitative interviews and retention rates during the study.
- Assess adherence to and completion of the intervention (i.e. do participants adhere and work through all components of the intervention) and explore engagement and satisfaction with the interventions by qualitative interviews.
- Assess the proportion of patients lost to follow-up after study entry.
- Assess safety of the interventions.
- Explore the appropriateness of outcome measures, completion rates and assess response to questionnaires through qualitative interviews.
- Evaluate the logistics of delivering a home-based tele-exercise training intervention through qualitative interview responses from both health care professionals and patients.
- Determine the “prehabilitation window” (length of time between MDT-conference and CABG surgery)

2.2 Secondary objective:

The secondary objectives will evaluate if the multimodal prehabilitation intervention has an impact on preoperative and postoperative outcomes. For this we will collect data on study outcomes to assess levels, variation, and changes over time, which can inform sample size for the future RCT, as shown in **Table 1**, section 7.2.

3. Method

[figure not shown]

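### Section 9.1 limits the analysis to description, then applies an unqualified P<0.05 rule to exploratory clinical outcomes, with no lead outcome named for the impact question in 2.2

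*Protocol*

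**What the plan says.** Section 9.1 begins: "Data analysis will be limited to descriptive summary statistics of the proposed endpoints", together with feasibility measures. The primary feasibility question is answered descriptively. The section then turns to the secondary aim, the response over time in "physical activity, muscle strength, functional capacity, body composition, quality of life and symptoms of depression, and anxiety". It ends: "A repeated measurements analysis will be used to analyze changes over time in continuous variables", with P "values <0.05 will be considered statistically significant". Neither sentence names a group term, a time point or an outcome that takes priority, and neither says that the p-values are exploratory.

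Other sections describe these outcomes more cautiously, with one exception:

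- Section 7: "we will explore two types of outcomes: feasibility outcomes and explorative clinical outcomes".
- Section 7.2: "data will be collected on the following explorative outcomes".
- Section 3.6: 25 patients per group, with no formal power calculation.
- Section 2.2 gives two purposes. One is estimation: "assess levels, variation, and changes over time, which can inform sample size for the future RCT". The other, the exception, is a question about effect: "The secondary objectives will evaluate if the multimodal prehabilitation intervention has an impact on preoperative and postoperative outcomes".

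**The concern.** A significance threshold is a decision rule, and it sits badly with a section that has just restricted itself to description, and with outcomes labelled explorative in an unpowered study. As written, any continuous outcome that crosses 0.05 may be called statistically significant, and 2.2 invites the reader to take that as an impact of the programme.

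Two things are at stake. First, with a dozen outcomes and none named as the lead, one chance result could be reported as an effect. Second, 2.2 says these data can inform the sample size of the full-scale trial. An effect picked because it stood out among many is biased upward, and a trial sized on it would be too small.

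**Working it through.** **1. The plan's own figure.** The only figure stated is the per-test threshold of 0.05. The protocol gives no overall error rate, number of tests or power, so there is nothing further to reproduce.

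**2. Counting the outcomes (Tables 1 and 2).** Ten continuous instruments have a baseline and at least one later measurement: 6MWT, sit-to-stand, hand grip, BIA, SENS activity, SF-12, HeartQoL, state anxiety, PHQ-4 and PAM13. SF-12 yields two summary scores and HeartQoL two subscales. With BIA counted once, that makes 10 + 2 = 12 scores. BIA components, SF-12 domains and the four blood markers are left out.

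**3. If the rule is applied to between-arm or group-by-time terms, one test per score.** Suppose the programme has no effect on any score.

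- Independent scores: 1 − 0.95^12 = 0.460.
- Correlated scores: let each null statistic be Z_i = √ρ·W + √(1−ρ)·E_i, with W and E_i independent standard normal, and find P(max|Z_i| > 1.96) over 12 scores.

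| Assumed correlation ρ | Chance of at least one P<0.05 |
|---|---|
| 0 | 46% |
| 0.3 | 40% |
| 0.5 | 32% |
| 0.7 | 23% |

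The protocol gives no correlations, so the range is shown. With ten instruments counted once each, the same calculation gives 40% down to 21%.

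**4. Sensitivity: each visit tested separately.** Hand grip and BIA have no day-30 mark in Table 2. The other 10 scores do, which gives 12 + 10 = 22 contrasts, leaving out the day-4 SENS reading. If all are independent, 1 − 0.95^22 = 0.68. With the two visits of one score correlated 0.5 (assumed), the chance is 65%, 58%, 49% and 37% for between-score correlations of 0, 0.3, 0.5 and 0.7.

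**5. Size of a selected effect.** With 25 per arm, the standard error of a standardised difference is √(2/25) = 0.283 SD. Under no effect, the mean of the largest |Z| among 12 scores at ρ = 0.5 is 1.76. The largest observed difference therefore averages 1.76 × 0.283 = 0.50 SD by chance alone. For comparison, power at 25 per arm is 18%, 42% and 81% for true differences of 0.3, 0.5 and 0.8 SD.

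**6. If the rule is applied to change over time alone.** Steps 3 to 5 do not apply, because the no-change null is not credible even with an inert programme. Section 1.2 describes CABG as improving exercise capacity and quality of life, so change to day 30 can be real in both arms. Section 1.2.1 says patients deteriorate functionally and psychologically while waiting, so change to the day before surgery can be real too. A significant change would be a true finding, but not one about prehabilitation.

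**The case against.** The strongest reply is that the exploratory status is already clear. Sections 7 and 7.2 say so, 3.6 disclaims a power calculation, and 9.1 answers the primary question descriptively. Exploratory secondary outcomes in a feasibility study do not need familywise error control, and a hierarchy, model contrast or key time point may properly sit in a statistical analysis plan that is not shown. All of that stands. The point is therefore not that an adjustment is missing. It is that the protocol states an unqualified significance rule that conflicts with its own opening sentence and its own labels.

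A second reply is that 9.1 plans only change over time, so no between-arm error rate arises. This stands as a limit on the figures: they are conditional on arms being compared. But a comparison of arms is clearly in view. Section 2.2 asks about impact, 9.1 lists improvement relative to usual care for patient-reported outcomes, and 3.4 has conclusions drafted twice, with each arm in turn assumed to be the intervention. If only change over time is tested, the rule cannot answer 2.2.

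A third reply is that the harm is speculative. The progression criteria in 7.1 rest on participation and intervention delivery, and nothing says that the later trial's outcome will be chosen by significance. That is correct, and it keeps the severity down.

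**Conclusion.** The point holds in a limited form. Section 9.1 contradicts itself by restricting the analysis to description and then adding a significance rule. That rule has no lead outcome to tie it to the impact question in 2.2. For between-arm or group-by-time tests, one per score on about 12 scores, the chance of at least one false significant effect is 23% to 46%, against 5% for a single test. This assumes a programme with no effect on any score and correlations between scores of 0.7 down to 0.

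Three stronger readings are tempting, and the documents do not support them:

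- A reader might infer that a false positive is likely, meaning more probable than not. With one test per score it stays below 50% throughout the range.
- A reader might take 22 tests as planned. The protocol plans a repeated-measurements analysis and does not say that each visit is tested separately, so the higher figures are a sensitivity only.
- A reader might apply the same error rate to change over time. It does not apply there, for the reason in step 6 of the working.

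Severity is minor to moderate. The feasibility conclusion does not depend on these tests. What is exposed is how clinical results are described and carried into the later trial.

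**What to change.** In 9.1, replace the closing P<0.05 sentence with:

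> Secondary clinical outcomes are exploratory and are reported for all outcomes and time points as between-arm estimates with 95% confidence intervals; any p-value is nominal, unadjusted for multiple comparisons, and will not be described as a statistically significant effect or used alone to choose the RCT primary outcome.

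This brings the end of 9.1 into line with its opening and with sections 7 and 7.2. It directs the analysis at the arm comparison that 2.2 asks about, and it still supplies the levels and variation needed to plan the later trial. It requires no multiplicity procedure.

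The cost is one sentence, with no extra patients or data. The downside is that individual secondary results can no longer be called statistically significant.
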